2.2. Statistical Hypothesis

For comparison of a single dose of REGN5713-5714-5715 to placebo, the following hypothesis of the primary endpoint (average CSMS over birch pollen season) will be tested:

- **H0**: There is no difference in CSMS, averaged over the duration of the birch pollen season, in subjects receiving REGN5713-5714-5715 and placebo.
- H1: The CSMS, averaged over the duration of the birch pollen season, is statistically significant different in subjects receiving REGN5713-5714-5715 and placebo.

The statistical hypothesis above is to test in a hierarchical procedure for primary efficacy and secondary endpoints at 2-sided 5% significance level.

2.3. Sample Size and Power Considerations

This study is powered to detect differences between REGN5713-5714-5715 and placebo on the primary endpoint of the average CSMS during birch pollen season. A sample size of 120 subjects per arm gives 90% power to detect a mean difference in average CSMS of 1.9 (30% reduction from placebo) in REGN5713-5714-5715 (mean CSMS = 4.4) and placebo (mean CSMS = 6.3),

assuming a common standard deviation in CSMS of 4.5 with a two-sample t-test at 2-sided significance level of 0.05. Assuming 20% drop out rate during the birch pollen season, the target is to randomize 150 subjects per arm.

Estimates of mean and variability of the CSMS are based on pooled estimates across several field studies for grass sublingual immunotherapy, and a 30% treatment effect relative to placebo is in line with what was observed in the phase 1b POC study for REGN5713-5714-5715.

This planned sample size (150 subjects per arm) also gives 93% power to detect a mean difference in TNSS of 0.6 (26% reduction from placebo) in REGN5713-5714-5715 (mean TNSS=1.7) and placebo (mean TNSS=2.3), assuming a common standard deviation in TNSS of 1.5 at 2-sided alpha of 0.05 using a two-sample t-test. The assumptions of TNSS endpoint are based on effects observed in the GT-08 trial of timothy grass sublingual tablet (Dahl, 2006). With the same mean for placebo and common standard deviation from GT-08 but a 30% reduction from placebo for REGN5713-5714-5715 as observed in the phase 1b POC study, the study will have a greater power.

The sample size and power calculations were performed using nQuery Advisor 7.0

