# **11.2.** Justification of Sample Size

This study is powered to detect differences between REGN5713-5714-5715 and placebo on the primary endpoint of the average CSMS during birch pollen season. A sample size of 150 enrolled subjects per arm gives 90% power to detect a mean difference in average CSMS of 1.9 (30% reduction from placebo) in REGN5713-5714-5715 (mean CSMS = 4.4) and placebo (mean CSMS = 6.3), assuming a common standard deviation in CSMS of 4.5. The minimum significant difference in CSMS is 1.14, or approximately an 18% reduction from placebo. This sample size calculation assumes a 20% drop out rate (30 subjects per arm) and a two-sample t-test with two-sided alpha of 0.05. Estimates of mean and variability of the CSMS are based on pooled estimates across several field studies for grass immunotherapy, and a 30% treatment effect relative to placebo is in line with what was observed in the phase 1b POC study for REGN5713-5714-5715.

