3.1. The Full Analysis Set (FAS)

The full analysis set (FAS) includes all randomized subjects who had at least 1 e-diary entry with symptoms or medication score recorded during the birch pollen season; it is based on the treatment allocated (as randomized). Since the TNSS, TOSS and DMS will be completed sequentially, all randomized subjects with at lease 1 TNSS e-diary entry will be included in FAS. Efficacy endpoints will be analyzed using the FAS.

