5.6.2. Analysis of Secondary Efficacy Variables

Secondary efficacy variables will be analyzed using linear mixed-effect model in the same fashion as the primary analysis for primary endpoint, average CSMS during birch pollen season. Subjects with at least 1 day of post-baseline diary record will be included in the analysis, and only days with observed data (including any available data of daily entries prior to subject discontinuation) will be included in the calculation of average score. Data after rescue will be utilized and data after relevant prohibited medications will be set to missing according to Table 2.

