5.6.3. Adjustment for Multiple Comparison

The following multiplicity adjustment approach, a hierarchical procedure, will be used to control overall Type-1 error rate at 0.05 for the primary endpoint and the secondary endpoints. Each hypothesis will be formally tested only if the preceding one is significant at the 2-sided 0.05 significance level. The hierarchical testing order is shown as follows.

- 1. **Primary endpoint**: Daily CSMS, averaged over the duration of the birch pollen season, in subjects who receive a single dose of REGN5713-5714-5715 versus placebo
- 2. TNSS, averaged over the duration of the birch pollen season, in subjects who receive a single dose of REGN5713-5714-5715 versus placebo
- 3. TSS, averaged over the duration of the birch pollen season, in subjects who receive a single dose of REGN5713-5714-5715 versus placebo
- 4. Change from baseline to the end of study in birch SPT mean wheal diameter in subjects who receive a single dose of REGN5713-5714-5715 versus placebo
- 5. Percent change from baseline to the end of study in birch SPT mean wheal diameter in subjects who receive a single dose of REGN5713-5714-5715 versus placebo
- 6. TOSS, averaged over the duration of the birch pollen season, in subjects who receive a single dose of REGN5713-5714-5715 versus placebo
- 7. DMS, averaged over the duration of the birch pollen season, in subjects who receive a single dose of REGN5713-5714-5715 versus placebo

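### SAP 2.3 gives CSMS power on 120 per arm after 20% dropout but TNSS power on all 150 randomised; on the same 120, TNSS power is 87%, against the 93% stated

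*SAP*

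**What the plan says.** SAP 2.3 (Sample Size and Power Considerations) makes two power statements.

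- **CSMS (primary).** "A sample size of 120 subjects per arm gives 90% power to detect a mean difference in average CSMS of 1.9", with SD 4.5 and a two-sample t-test at two-sided 0.05. Dropout is then added: "Assuming 20% drop out rate during the birch pollen season, the target is to randomize 150 subjects per arm".
- **TNSS (secondary).** "This planned sample size (150 subjects per arm) also gives 93% power to detect a mean difference in TNSS of 0.6", with SD 1.5, the same test and the same alpha. The assumed means are 1.7 and 2.3, a 26% reduction. The section adds that a 30% reduction, attributed to the phase 1b study, would give greater power, without a figure.

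Protocol 11.2 starts from 150 enrolled per arm and says of its CSMS calculation: "This sample size calculation assumes a 20% drop out rate (30 subjects per arm". It adds: "The minimum significant difference in CSMS is 1.14, or approximately an 18% reduction from placebo".

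Both endpoints are analysed on the full analysis set. Under SAP 3.1, "all randomized subjects with at lease 1 TNSS e-diary entry will be included in FAS". In the testing order of SAP 5.6.3, TNSS comes directly after CSMS and ahead of TSS, the two skin prick test endpoints, TOSS and DMS. The rule is: "Each hypothesis will be formally tested only if the preceding one is significant at the 2-sided 0.05 significance level".

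**The concern.** Two powers in one section rest on different sample sizes. The 20% loss is charged to CSMS and not to TNSS, and the SAP does not say why. The TNSS sentence names its 150 per arm, but it does not tell the reader that the section's own dropout assumption has been left out.

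This matters because TNSS is the gate to five formally tested endpoints. If its power is overstated, so is the prospect of reaching any of them. The printed figures also make TNSS look better powered than the primary endpoint (93% against 90%), and that ordering comes from the change of basis.

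**Working it through.** **Inputs.** CSMS: difference 1.9, SD 4.5. TNSS: difference 0.6, SD 1.5, placebo mean 2.3. Two-sided alpha 0.05, two-sample t-test, 20% dropout (all SAP 2.3). 1:1 allocation (SAP 2.1). 30 dropouts per arm and minimum significant CSMS difference 1.14 (Protocol 11.2).

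**Formula.** With n per arm, df = 2n − 2 and noncentrality λ = difference / (SD × √(2/n)). Power is the probability that a noncentral t variable with these parameters lies beyond ± t(0.975, df).

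**Step 1: reproduce the plan's figures.**
- Dropout: 120 / (1 − 0.20) = 150. Reproduced.
- CSMS at n = 120: λ = 1.9 / (4.5 × √(2/120)) = 3.27, power 90.3%. The stated 90% is reproduced.
- TNSS at n = 150: λ = 0.6 / (1.5 × √(2/150)) = 3.46, power 93.2%. The stated 93% is reproduced.

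**Step 2: which n does the protocol's CSMS calculation use?** The minimum significant difference is t(0.975, 2n − 2) × 4.5 × √(2/n).
- n = 120: 1.144, matching the stated 1.14.
- n = 150: 1.023, which does not match.

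So the protocol's CSMS figures, like the SAP's, are on 120 per arm.

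**Step 3: put both endpoints on one basis.**

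| Endpoint and difference | n = 120 | n = 150 |
|---|---|---|
| CSMS 1.9 (30% reduction) | 90.3% | 95.4% |
| TNSS 0.6 (26% reduction) | 87.0% | 93.2% |
| TNSS 0.69 (30% × 2.3) | 94.4% | 97.8% |

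For the effects to which the SAP attaches its printed powers, TNSS is below CSMS at either n. The chance of missing TNSS at 0.6 is 1 − 0.870 = 13.0% on 120, against 1 − 0.932 = 6.8% on 150.

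**Step 4: how many must be analysed for the stated 93%?** TNSS power at 0.6:

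| n per arm | Power |
|---|---|
| 132 | 89.9% |
| 133 | 90.1% |
| 135 | 90.6% |
| 145 | 92.4% |
| 146 | 92.6% |

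Power reaches 90% at 133 per arm and rounds to 93% only from 146. That needs 146 − 120 = 26 of the 30 assumed dropouts per arm to contribute in-season TNSS data.

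**Step 5: the 30% attribution (side point).** SAP 2.3 presents the 30% TNSS reduction as a phase 1b observation. Protocol 1.3 reports reductions in nasal-challenge TNSS AUC of 32%, 27% and 19% at days 8, 29 and 57. None is 30%, and the day-57 value is below the 26% assumed for TNSS.

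**The case against.** The strongest reply is that 150 may be nearer the truth for TNSS. The SAP places dropout within the pollen season, the diary starts at randomisation about two weeks before it, and one in-season TNSS entry puts a subject in the full analysis set. SAP 5.6.2 uses observed days, "including any available data of daily entries prior to subject discontinuation". Someone who leaves mid-season after making entries is therefore still analysed, and 120 may simply be conservative.

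This is right about the analysis rules, and it is why the TNSS figure is best read as a range of 87% to 93%. It does not rescue the two bases. CSMS is analysed on the same set, so if partial diaries justify 150 for TNSS, they justify 150 for CSMS, whose power is then 95%.

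Other points also have some force:

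- **The 150 is labelled, and 93% is correct for it.** True: this is an inconsistent basis and not a miscalculation.
- **The comparison with CSMS sets a 26% reduction against a 30% one.** At 30% for both, TNSS has the higher power (94.4% against 90.3% at 120). But the SAP attaches its 93% to the 0.6 difference and gives no figure for 0.69.
- **The 30% may be only a rounded planning value.** The first two phase 1b results lie on either side of it, so the wording is loose and not grossly wrong. The main point does not depend on it.
- **TNSS does not drive the sample size.** True. Neither the estimate nor the Type I error is touched.

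**Conclusion.** The concern holds. On the section's own 20% dropout assumption, TNSS power for the stated effect is 87%, about 6 points below the printed 93%, and the chance of missing the effect is 13%, nearly double the implied 7%. This rests on the SAP's difference of 0.6 and SD of 1.5, a two-sample t-test and 120 analysed per arm. If more of the assumed dropouts contribute in-season data, power rises towards 93%; if the true reduction is 30%, it is 94% even on 120. The planned enrolment remains sound for CSMS. What needs correcting is a stated operating characteristic of the endpoint that gates the rest of the testing sequence, so the change should be made, although it does not threaten the trial's validity.

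**What to change.** In SAP 2.3:

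1. State TNSS power as 87% on 120 evaluable subjects per arm (94% for a 30% reduction), the same basis as CSMS. Give 93% beside it as the figure if at least 146 of 150 per arm contribute in-season TNSS data.
2. Describe the 30% TNSS reduction as an assumption, and list the reported phase 1b nasal-challenge values: 32%, 27% and 19% at days 8, 29 and 57.

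The cost is two sentences in the SAP. No protocol change is needed, and enrolment, testing order and analysis stay as they are. The only downside is a less favourable stated TNSS power.

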2. INVESTIGATION PLAN

2.1. Study Design and Randomization

This is a phase 3 multi-center, randomized, double-blind, placebo-controlled, parallel group study to assess the efficacy of REGN5713-5714-5715 to reduce allergic rhinitis (nose) and conjunctivitis (eye) symptoms and the use of rescue medications during birch pollen season.

Efficacy will be evaluated by assessing the reduction of allergic nose and eye symptoms and the reduction in the use of allergy rescue medications during birch pollen season, after a single SC dose of REGN5713-5714-5715 or placebo. The incidence and severity of TEAEs, including hypersensitivity reactions and local injection site reactions, will also be assessed. Total concentration in serum and immunogenicity of REGN5713, REGN5714, and REGN5715 will be measured throughout the study.

Subjects will be randomized according to a central randomization scheme provided by interactive response Technology (IRT) to the designated study pharmacist (or qualified designee). Subjects will be randomized 1:1 as below:

- REGN5713-5714-5715
- Matching placebo

Randomization will be stratified based on the following:

- Serum specific birch pollen IgE levels at screening (<17.5 kUa/L versus ≥17.5 kUa/L)
- In North America only: Serum specific oak pollen IgE levels at screening (<0.7 kUa/L versus ≥0.7 kUa/L)
- Geographical region (North America (NA) versus Europe (EU))

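### The 93% TNSS power in SAP 2.3 is a stand-alone figure at 150 per arm that leaves out both the 20% dropout applied to CSMS and the CSMS gate in SAP 5.6.3; on the CSMS basis of 120 it is 87% stand-alone and about 81% to 85% in sequence

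*SAP*

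**What the plan says.** SAP 2.3 gives two power statements on different numbers of subjects.

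- **CSMS (primary):** "A sample size of 120 subjects per arm gives 90% power to detect a mean difference in average CSMS of 1.9", "assuming a common standard deviation in CSMS of 4.5 with a two-sample t-test at 2-sided significance level of 0.05". The allowance for loss follows: "Assuming 20% drop out rate during the birch pollen season, the target is to randomize 150 subjects per arm".
- **TNSS (first secondary):** "This planned sample size (150 subjects per arm) also gives 93% power to detect a mean difference in TNSS of 0.6", "assuming a common standard deviation in TNSS of 1.5 at 2-sided alpha of 0.05 using a two-sample t-test". The section then remarks that power would be greater if TNSS fell by 30% instead of 26%, without giving a figure.

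SAP 2.2 announces hierarchical testing of the primary and secondary endpoints. SAP 5.6.3 sets the order, with CSMS first and TNSS second, and the rule: "Each hypothesis will be formally tested only if the preceding one is significant at the 2-sided 0.05 significance level". No power is given for the sequence, and neither document gives a correlation between CSMS and TNSS.

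**The concern.** TNSS is the first secondary claim and the only secondary endpoint with a printed power. A reader of the sample size section will take 93% as the chance that the trial can claim TNSS. It is the chance that a TNSS t-test, run on its own with every randomised subject contributing, would be significant.

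The plan differs from that in two ways. For CSMS it counts on 120 per arm, not 150. It also allows a TNSS claim only when CSMS and TNSS are both significant, and the probability of that cannot exceed the smaller of the two marginal powers. At stake is the accuracy of a stated operating characteristic. Type I error control and the validity of the tests are not in question.

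**Working it through.** **Inputs**

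- CSMS: difference 1.9, SD 4.5 (SAP 2.3).
- TNSS: difference 0.6, SD 1.5 (SAP 2.3). The 30% scenario is 0.30 × 2.3 = 0.69, using the placebo mean in SAP 2.3.
- Two-sided alpha 0.05 and a two-sample t-test for each (SAP 2.3); 1:1 allocation (SAP 2.1).
- n per arm: 150 randomised; 150 × 0.8 = 120 after dropout (SAP 2.3).
- Fixed sequence, CSMS then TNSS, each at 0.05 (SAP 5.6.3).
- Correlation ρ between subject-level average CSMS and average TNSS: not in the documents. I assume 0.5 to 0.9 and also show 0 and 1. A positive value is expected because average TNSS is one of the three terms summed to give average CSMS (SAP 4.5.1).

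**Step 1. Reproduce the printed figures.** Stand-alone power comes from the noncentral t distribution with 2n − 2 degrees of freedom and noncentrality (difference/SD) × √(n/2).

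- CSMS, n = 120: (1.9/4.5) × √60 = 3.271, critical value 1.970, power 90.3%. This matches the printed 90%.
- TNSS, n = 150: (0.6/1.5) × √75 = 3.464, critical value 1.968, power 93.2%. This matches the printed 93%.

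**Step 2. Put both endpoints on the same n.**

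| n per arm | CSMS stand-alone | TNSS stand-alone (0.6) |
|---|---|---|
| 120 | 90.3% | 87.0% |
| 150 | 95.4% | 93.2% |

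Moving TNSS from 150 to 120 costs 93.2 − 87.0 = 6.2 points, before any gate.

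**Step 3. Apply the gate.** The chance of claiming TNSS is P(CSMS significant and TNSS significant). I approximate it by the standard bivariate normal distribution function with correlation ρ, evaluated at (z₁ − c, z₂ − c). Here z = (difference/SD) × √(n/2) and c is the t critical value. For n = 120 the arguments are 3.271 − 1.970 = 1.301 and 3.098 − 1.970 = 1.128. For n = 150 they are 1.689 and 1.496.

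| ρ | n = 120 | n = 150 |
|---|---|---|
| 0 | 78.6% | 89.0% |
| 0.5 | 81.2% | 90.1% |
| 0.6 | 81.9% | 90.5% |
| 0.7 | 82.7% | 90.9% |
| 0.8 | 83.7% | 91.5% |
| 0.9 | 85.0% | 92.2% |
| 1 (ceiling) | 87.0% | 93.3% |

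Using 1.96 as the critical value raises the ρ = 0.5 to 0.9 results by 0.1 to 0.3 points. Simulating the two t-tests (20,000 trials per setting) agreed to within about 0.6 points.

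**Step 4. Split the shortfall.**

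- At 120, the total is 93.2 − 85.0 = 8.2 points (ρ = 0.9) to 93.2 − 81.2 = 12.0 points (ρ = 0.5). Dropout accounts for 6.2 of this. The gate accounts for 87.0 − 85.0 = 2.0 to 87.0 − 81.2 = 5.8.
- At 150, the gate alone costs 93.2 − 92.2 = 1.0 to 93.2 − 90.1 = 3.1 points.

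**Step 5. The 30% TNSS scenario (0.69), with CSMS still at 1.9.**

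| n per arm | TNSS stand-alone | In sequence, ρ = 0.5 to 0.9 |
|---|---|---|
| 120 | 94.4% | 86.8% to 89.4% |
| 150 | 97.8% | 93.9% to 95.0% |

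**The case against.** The strongest reply is that SAP 2.3 contains no arithmetic error. It states the number of subjects, effect, SD, alpha and test behind the 93%, the figure reproduces, and the section never calls it power under the hierarchy. That stands: the point concerns what the figure leaves out.

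A reader might infer that 90% for CSMS and 93% for a test gated by CSMS contradict each other. The documents do not support this, because the two figures use different numbers of subjects. At 150 per arm the gate has 95.4% power, above 93.2%, so the gate does not put the TNSS figure out of bounds on a common n. Nor should the whole shortfall be blamed on the gate: at 120, dropout accounts for about 6 of the 8 to 12 points.

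A reader might also infer that the testing rule can never give 93%. That goes too far. At the stated difference of 0.6, the sequence stays below the stand-alone figure for any correlation under 1. Under the 30% scenario in the same paragraph, with 150 per arm, it gives about 94% to 95%.

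It is also fair to say that 120 may be pessimistic. The full analysis set in SAP 3.1 keeps any randomised subject with one in-season TNSS entry, and SAP 2.3 places the dropout within the season. The analysed number could therefore lie between 120 and 150. For that reason both ends are shown. Even so, 120 is the SAP's own planning number for CSMS, and TNSS should not be planned on a more favourable one without saying so.

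Finally, the trial is sized on CSMS alone (Protocol 11.2), so no design decision rests on the TNSS figure. That limits the weight of the point but does not remove it.

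**Conclusion.** The point holds as one of incomplete reporting. The 93% is a correct marginal power at 150 per arm, but it omits the dropout allowance used for CSMS in the same section and the gate in SAP 5.6.3. On the CSMS basis of 120 per arm, stand-alone TNSS power is 87%, and the chance of claiming TNSS is about 81% to 85%. If all 150 per arm are analysed, that chance is about 90% to 92%.

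The sequence figures rest on an assumed correlation of 0.5 to 0.9, on the SAP's own effects and SDs, and on t-tests standing in for the planned mixed model, as SAP 2.3 itself does. The 87% needs no correlation. The direction of the gate effect holds for any correlation below 1, but its size depends on the value.

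**What to change.** In SAP 2.3:

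1. Label the 93% as marginal TNSS power at 150 per arm, before dropout and before the CSMS gate.
2. Add the figures on the CSMS basis: 87% marginal at 120 per arm, and about 81% to 85% (120) to 90% to 92% (150) for declaring both CSMS and TNSS significant under SAP 5.6.3. State the correlation range of 0.5 to 0.9 as an assumption.
3. Replace the unquantified remark on the 30% TNSS reduction with the same pair of figures: 94% marginal and about 87% to 89% in sequence at 120; 98% marginal and about 94% to 95% in sequence at 150.

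The cost is a few sentences, a short calculation and a less favourable headline figure. Sample size, alpha, testing order and analyses stay as they are.

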2.4. Study Plan

The total study duration is approximately 28 weeks including screening, dependent on the start and end times of the local birch pollen season (Figure 1). The length of birch pollen season will vary based on geography. Approximately 300 birch-allergic subjects will be randomized 1:1 to REGN5713-5714-5715 or placebo.

The Schedule of Event table is presented in Section 10.2.

Figure 1: Study Flow Diagram

Birch pollen season February – June (depending on location)

3. ANALYSIS POPULATIONS

In accordance with guidance from the International Conference of Harmonization of Technical Requirements for Registration of Pharmaceuticals for Human Use (ICH) guideline ICH E9 Statistical Principles for Clinical Trials (ICH, 1998), the following population of analysis will be used for all statistical analysis.

3.1. The Full Analysis Set (FAS)

The full analysis set (FAS) includes all randomized subjects who had at least 1 e-diary entry with symptoms or medication score recorded during the birch pollen season; it is based on the treatment allocated (as randomized). Since the TNSS, TOSS and DMS will be completed sequentially, all randomized subjects with at lease 1 TNSS e-diary entry will be included in FAS. Efficacy endpoints will be analyzed using the FAS.

3.2. The Safety Analysis Set (SAF)

The safety analysis set (SAF) includes all randomized subjects who received any study drug; it is based on the treatment received (as treated). Treatment administration and all clinical safety variables will be analyzed using the SAF.

3.3. The Pharmacokinetic Analysis Set (PKAS)

The PK analysis set includes all treated subjects who received any study drug (safety population) and had at least 1 non-missing serum drug concentration following at least a single dose of REGN5713-5714-5715. Subjects will be analyzed according to the treatment actually received.

